2. To assess adverse events following cholecystectomy (e.g., bile duct injury) and their management.
3. To analyse rates and outcomes of unsuspected gallbladder cancer.
4. To evaluate the global variation in the availability of cholecystectomy services and training amongst included hospitals.
5. To assess sustainable practices in laparoscopic cholecystectomy globally.

AUDIT STANDARDS

Pre-operative

1. **Interventional radiology service:** There should be 24-hour access to interventional radiology to support the delivery of an emergency HPB service [11].
2. **Risk Stratification:** For patients with acute cholecystitis, surgeons may use the Tokyo Guidelines 18 (TG18) [8].
3. **Timing of surgery:** In patients presenting with acute cholecystitis, the optimal timing for cholecystectomy is within 48 hours, and no more than 10 days from symptom appearance [7].

Intra-operative

1. **Critical Safety View (CVS):** The use of the CVS during laparoscopic cholecystectomy (achieving all 3 components – Figure 1) is the recommended approach to correctly identify relevant anatomy and minimize the risk of bile duct injuries [7,8]:
 - I. **Clearance of the hepatocystic triangle:** The HC triangle should be cleared of all the fibro-fatty and soft areolar tissue.
 - II. **Exposure of the lower cystic plate:** The gallbladder should be separated from its liver bed to expose at least the lower third of the cystic plate.
 - III. **Only two tubular structures should be seen entering the gallbladder:** the cystic duct and the cystic artery.

[figure not shown]

Figure 1: Photographs showing the critical view of safety.

2. **Intraoperative imaging:** in patients with uncertainty of biliary anatomy or suspicion of bile duct injury, intraoperative imaging (e.g. cholangiogram, laparoscopic ultrasound and incisionless cholangiography with fluorescence) may help delineate relevant anatomy, detect bile duct stones, and decrease the risk of bile duct injury [7,8,12].
3. **Bailout Procedures:** When CVS cannot be achieved and the biliary anatomy cannot be clearly defined by other methods (e.g. imaging) during laparoscopic cholecystectomy, surgeons should

consider a bailout procedure (e.g. subtotal cholecystectomy or total cholecystectomy by the fundus-first (top down) approach) [7].

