Validation by primary data collection teams:

- Follow-up methodology at patient level: all hospitals will self-report the methods used to determine 30-day outcomes.
- Patient identification methodology: all hospitals will self-report the methods used to identify patients who fulfil the inclusion criteria.

Validation by independent teams:

- Case ascertainment: hospital records will be reviewed to identify patients fulfilling the inclusion criteria within a 2-week data collection period and comparing this to the actual number of cases submitted. This will be performed by individuals not involved in collecting the primary data. By comparing samples, a quantitative estimate of case ascertainment will be produced by the central data team.
- Data accuracy: a subset of collected variables will be validated by individuals who are independent of the primary data collection process. Following the “case ascertainment” stage, validators will be asked to provide data for a subset of variables, two patient variables, two operation variables, and two outcome measures.

Project Team Structure

Each registered centre must have a supervising consultant/attending to ensure adequate data quality. In the case that the hospital lead is a registrar/resident then they must recruit a consultant/attending to supervise the study. The hospital lead should also ensure that they recruit independent data validators (registrars/residents or consultants/attendings) to perform the data validation outlined in the section above.

For data collection, the hospital lead should recruit a “mini-team” of up to five local collaborators for each data collection period (**Table 1; page 15**). Medical students, doctors (non registrars/residents or consultants/attendings) and nurses can act as local collaborators and their participation is encouraged. The same “mini-team” can cover different time periods at each hospital if they wish to. Each team should include at least one qualified doctor to provide additional local support for participating medical students or nurses. Additional collaborators can be recruited to aid one-year follow-up data collection once the follow-up period begins (31st Jul 2024). A detailed specification of each role can be found below (see **pages 23-24**).

STATISTICAL CONSIDERATIONS

Primary Outcome Measure

The primary endpoint of this study is the compliance to pre-, intra-, and post-operative audit standards (see pages 9-10).

Secondary Outcome Measures

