	USS:  Yes  No - not available  No - not indicated  No - patient declined  Unknown CT:  Yes  No: not available  No: not indicated  No: patient declined  Unknown MRCP:  Yes  No: not available  No: not indicated  No: patient declined  Unknown ERCP:  Yes  No: not available  No: not indicated  No: patient declined  Unknown EUS:  Yes  No: not available  No: not indicated  No: patient declined  Unknown HIDA:  Yes  No: not available  No: not indicated  No: patient declined  Unknown							
	Preoperative imaging (Tick all that apply)	 Gallstones  Thick-walled gallbladder  Pericholecystic fluid  CBD stones  Dilated CBD (Diameter: -- . -- mm (1dp))						
Imaging findings	First symptom onset and admission: -- -- Diagnosis and decision to operate: -- -- Decision to operate and surgery: -- --		Urgency of surgery  Elective  Delayed  Emergency (patient was on elective waiting list?)  Yes  No					

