10. Preoperative imaging findings*	
*Only for USS / CT / MRCP, what are the findings (tick all that apply): Gallstones Thick-walled Gallbladder (≥3mm or reported as thick walled) Pericholecystic fluid CBD stones Dilated CBD. If yes: CBD diameter (record in mm, to one decimal)

11. Days between first biliary symptom onset and admission	Number of days (Whole number, day 0 is same day of first symptom onset)

12. Days between diagnosis and decision to operate	
Number of days (Whole number, day 0 is same day of diagnosis)
 
Guide for decision to operate day:
 
 For elective cases this should be the day the patient was seen in the outpatient clinic. For delayed cases this is the day the patient was LAST discharged from hospital with biliary disease. For emergency cases this should be the day the decision was made to perform an acute cholecystectomy in that emergency admission. If the patient was previously on an elective waiting list for surgery, please still use the date it was decided to perform the operation as an emergency.
13. Days between decision to operate and surgery performed	
Number of days (Whole number, day 0 is same day as surgery)

14. Urgency of surgery (Appendix D for definitions)	
Elective Delayed Emergency. If yes: Was the patient already on the elective waiting list for surgery? (Yes / No)

15. Indication for surgery (Appendix D for definitions)	
Acute calculous cholecystitis. If yes: Tokyo grade: I / II / III (Was the Tokyo grade documented in patient notes: Yes / No) Biliary colic Acalculous cholecystitis Chronic calculous cholecystitis Common Bile Duct (CBD) stone Gallbladder polyp Dyskinesia Gallstone pancreatitis. If yes: Atlanta criteria: mild / moderate / severe (Was the Atlanta criteria documented in patient notes: Yes / No)

Intra-operative Data Fields	Required data (definition / comment)
1. Mode of Anaesthesia* (Select all that apply)	
Local (subcutaneous / intraperitoneal) Regional (spine-related / regional nerve block) Sedation (e.g., midazolam) General Inhaled (sevoflurane / halothane / desflurane / Nitric Oxide (N2O) / isoflurane) Total Intravenous Volatile Anaesthetic (TIVA) *This refers to the anaesthetic used during the operation and NOT as induction agents

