6. **Living With Moderate Frailty:** People need help with all outside activities and housekeeping. Inside often have problems with stairs, need help with bathing, and may need minimal assistance with dressing.
7. **Living With Severe Frailty:** Completely dependent for cognitive and physical personal care. However, they seem stable and not at high risk of dying (within six months).
8. **Living with Very Severe Frailty:** Completely dependent for personal care and approaching end of life. Typically, they could not recover even from minor illnesses.
9. **Terminally Ill:** Approaching the end of life. This category applies to people with a life expectancy of under six months who are not otherwise living with severe frailty.

Indication for Surgery

Indication	Definition
Biliary colic	The presence of colicky right upper quadrant pain associated with gallstones or sludge on an USS, but no signs of acute cholecystitis [23]
Acute calculous cholecystitis	Clinical (right upper quadrant pain, with or without fever, WCC > 11 × 10 ⁹ /l) OR ultrasound evidence (thick walled gallbladder (≥ 3mm), OR USS tenderness over the gallbladder, the presence of gallstones) [23,24]
Acute acalculous cholecystitis	Clinical OR ultrasound evidence (thick walled gallbladder and/or pericholecystitis, USS tenderness over the gallbladder) in the absence of gallstones [23]
Chronic calculous cholecystitis	Previous clinical or ultrasound evidence (thick walled gallbladder and/or pericholecystitis, OR USS tenderness over the gallbladder OR the presence of gallstones) of cholecystitis [23]
Common bile duct stone	Common bile duct stones, as confirmed by before or at the time of surgery
Gallbladder polyp	Hyperechoic lesions on USS imaging which have no acoustic shadow and do not move with positional changes, with no overt features of malignancy [25]
Dyskinesia	Biliary like abdominal pain, occurring in a normal appearing gallbladder with a functional HIDA scan showing an abnormal gallbladder ejection fraction of less than 40% [26,27]

Tokyo Guidelines 2018 for Grading of Acute Cholecystitis

Tokyo guidelines 2018 grading [24] are listed below:

- **Grade I (mild):** No organ dysfunction and mild inflammatory changes in the gallbladder.
- **Grade II (moderate):**
 - Elevated WBC count (>18,000/mm³)
 - Palpable tender mass in the right upper abdominal quadrant
 - Duration of complaints >72 hours

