 - Marked local inflammation (gangrenous cholecystitis, pericholecystic abscess, hepatic abscess, biliary peritonitis, emphysematous cholecystitis)
- **Grade III (severe):**
 - Cardiovascular dysfunction: hypotension requiring treatment with dopamine ≥5 µg/kg per min, or any dose of norepinephrine
 - Neurological dysfunction: decreased level of consciousness
 - Respiratory dysfunction: PaO₂/FiO₂ ratio <300
 - Renal dysfunction: oliguria, creatinine >2.0 mg/dl
 - Hepatic dysfunction: PT-INR >1.5
 - Hematological dysfunction: platelet count <100,000/mm³

Revised Atlanta Criteria for Acute Pancreatitis

Atlanta Criteria [28] is listed below:

- **Mild:** No organ failure. No local complications (e.g., necrosis or collection). No systemic complications.
- **Moderate:** Transient organ failure (<48 hours) OR Local/systemic complications
- **Severe:** Persistent organ failure

Urgency of Surgery

The urgency of index cholecystectomy is defined as [3]:

- **Elective:** planned elective admission for cholecystectomy via a routine surgical waiting list from the outpatient department only. Patients on an elective waiting list treated as an emergency should be classed as ‘acute’ cases.
- **Delayed:** all other planned cholecystectomies; for example, patients who have had one or more acute admissions with biliary symptoms, but then discharged for a planned procedure on an elective operating list.
- **Emergency:** emergency admission with biliary disease through the Emergency Department or primary care, and cholecystectomy performed during that emergency admission.

Nassar Grade of Operative Difficulty

[figure not shown]
Grade [29]	Gallbladder	Cystic pedicle	Adhesions
I	Floppy, non-adherent	Clear, thin	Simple, up to neck and Hartmann’s pouch
II	
 • Mucocele • Packed with stones 	Fat-laden	Simple, up to the body
III	
 • Deep fossa • Acute cholecystitis • Contracted, fibrous Hartmann’s pouch adherent to CBD or with stone impaction 	
 • Abnormal anatomy • Cystic duct short, dilated or obscured 	
 • Dense, up to the fundus • Involving hepatic flexure or duodenum
IV	
 • Completely obscured • Empyema/gangrene • Mass 	Impossible to clarify	Dense, fibrous, wrapping the gallbladder. Duodenum or hepatic flexure is difficult to separate

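### The timing-of-surgery standard in the primary endpoint cannot be scored reliably for every patient from the intervals collected

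*Protocol*

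**What the plan says.** Protocol, Primary Outcome Measure: "The primary endpoint of this study is the compliance to pre-, intra-, and post-operative audit standards". The third pre-operative standard (Audit Standards, Timing of surgery) says that, for those who present with acute cholecystitis, "the optimal timing for cholecystectomy is within 48 hours, and no more than 10 days from symptom appearance".

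The inputs are pre-operative fields 11 to 13 of Appendix B, repeated in Section 1 of the case report form (Appendix A):

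- Field 11 runs from the first biliary symptom to admission. The form labels it "First symptom onset and admission", and the dictionary defines the unit as "Number of days (Whole number, day 0 is same day of first symptom onset").
- Field 12 is "Days between diagnosis and decision to operate". For delayed cases the decision day is set at the last discharge with biliary disease.
- Field 13 runs from the decision to the operation, again in whole days.

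The section on control of bias and confounding points to Appendix B, and to the REDCap database, for the complete list of fields. Appendix B contains no admission, diagnosis or operation date.

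Two definitions in Appendix D bear on the denominator. Delayed surgery includes "patients who have had one or more acute admissions with biliary symptoms, but then discharged for a planned procedure on an elective operating list". Chronic calculous cholecystitis rests on "Previous clinical or ultrasound evidence" of cholecystitis.

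**The concern.** The standard is about elapsed time from symptom appearance to surgery, but the form never asks for that time. It has to be assembled from pieces, and the pieces do not join: one ends at admission and the next starts at diagnosis. Diagnosis is not defined. The starting point is the first biliary symptom, with nothing to restrict it to the acute episode that led to surgery. The unit is the whole day, while one limit is in hours. The standard also does not say clearly whether the 48 hours run from symptoms, admission or diagnosis.

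There is a separate question about who is counted. The standard applies to patients who present with acute cholecystitis. A patient who presented acutely, went home and had surgery later can satisfy the chronic definition. If coded that way, a patient who probably missed the limit is no longer in the denominator.

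The study aims to describe variation between health systems. Earlier colic, time to diagnosis and deferral may all differ between systems, so these errors could be mistaken for differences in compliance. An analysis plan can choose a derivation rule, but it cannot supply an interval that was not recorded.

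**Working it through.** The protocol gives no computed figure on this point, so the check is whether the component can be derived.

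**1. The missing interval.** Let a = first symptom to admission (field 11), g = admission to diagnosis (not recorded), b = diagnosis to decision (field 12) and c = decision to surgery (field 13). Onset-to-surgery time is T = a + g + b + c, but only S = a + b + c is known. The 10-day limit requires S + g ≤ 10. Assume g lies between -2 and +3 days; it is negative when diagnosis precedes admission.

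| Recorded S | Values of g that meet the limit | Class fixed? |
|---|---|---|
| 7 or less | all (7 + 3 = 10) | yes, within |
| 8 | -2 to +2 | no |
| 9 | -2 to +1 | no |
| 10 | -2 to 0 | no |
| 11 | -2 to -1 | no |
| 12 | -2 only | no |
| 13 or more | none (13 - 2 = 11) | yes, beyond |

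The range for g is an assumption and may be too narrow. Field 12 expressly covers emergency patients already on an elective waiting list. If a site takes their diagnosis to be the earlier gallstone diagnosis, g is negative by an unrecorded amount and S can overstate T without a known bound.

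**2. The 48-hour limit.** A calendar difference of k days spans more than 24(k - 1) and less than 24(k + 1) hours, with a floor of 0.

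- k = 0 or 1: at most 48 hours, so within.
- k = 2: 24 to 72 hours, so undetermined. With uniform clock times on both days (assumed), the simulated share within 48 hours is 0.50.
- k = 3 or more: at least 48 hours, so beyond.

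The start point also decides which fields are needed. From symptoms the time is a + g + b + c, and from admission it is g + b + c; both contain the missing term. Only a count from diagnosis, b + c, avoids it.

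**3. The starting symptom.** Take a patient admitted one day after acute onset, with diagnosis and decision that same day and surgery on the next. True T = 1 + 0 + 0 + 1 = 2 days. If colic began 30 days before the acute onset and field 11 is read literally, a = 31 and S = 31 + 0 + 1 = 32. With 90 days, S = 91 + 0 + 1 = 92. Both are scored as beyond 10 days.

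**4. The denominator.** Let f be the share of acute presenters who are deferred beyond the limit and coded chronic, and p the compliance among those who remain. Compliance among all acute presenters is p(1 - f), so the reported figure is too high by the factor 1/(1 - f). With p = 80% (assumed):

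- f = 10%: 0.80 × 0.90 = 72%
- f = 30%: 0.80 × 0.70 = 56%
- f = 50%: 0.80 × 0.50 = 40%

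The documents give neither p nor f.

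**The case against.** The strongest reply is that much of the standard survives. Sums well away from the limit keep their class, and if diagnosis falls on the day of admission then g = 0 and the three intervals join. An emergency case with more than 10 days from decision to surgery is late whatever the gap. A reader might infer that the standard cannot be scored at all; the fields do not support that.

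A reader might also infer that field 11 certainly starts at the wrong symptom. It is paired with admission, and earlier disease has its own items (history, and biliary admissions in the prior year), so a site could take it to mean the first symptom of this presentation. The defect is ambiguity. That does not cure it, because sites that read the field differently will record different quantities. The other items allow only a partial sensitivity analysis, since colic that never led to admission appears in neither.

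A third tempting inference is that deferred patients are lost. They are eligible, flagged as Delayed, and have an unbroken diagnosis-to-decision-to-surgery interval. The risk lies in the indication code: the chronic definition permits that coding but does not require it. A statistical analysis plan may also set a denominator rule from urgency and history. Recovery that way is incomplete, because the history item is undated and pools acute cholecystitis with cholangitis.

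Finally, timing is one of eleven listed standards, no composite is stated, and the Data Analysis section says that attainment of some standards is not a definitive quality measure. This lowers the stakes but does not make the component derivable.

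**Conclusion.** The point holds in a limited form. From the fields collected, the timing standard cannot be scored reliably for all patients, and no analysis plan could repair that, because the admission-to-diagnosis interval and the underlying dates are not held. The unreliable cases are recorded sums of 8 to 12 days at the 10-day limit (for an assumed gap of -2 to +3 days), calendar differences of 2 days at the 48-hour limit, and patients with earlier biliary symptoms wherever field 11 is read literally. How many patients fall in these groups cannot be worked out from the protocol.

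The denominator effect is a secondary coding risk. Its size, 1/(1 - f), depends on a share that the documents do not give and assumes that everyone so coded missed the limit.

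This is a should-fix: a component of the primary endpoint is affected, but many cases remain classifiable and it is one standard among several.

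**What to change.** 1. Keep field 11 as a measure of access delay, but word it for the index episode.
2. Add one field: the interval from onset of the index acute episode to start of surgery, in days, plus hours where known when it is 3 days or less. Collect it for emergency and delayed cases. The missing gap then drops out.
3. Add one yes/no item for delayed cases asking whether the index episode was acute cholecystitis. Define the denominator by this item rather than by the undated, pooled history field.
4. Reconcile the wording of the standard with the form and the dictionary, and state where the 48 hours start. This is a matter of measurement; no clinical timing rule is proposed.

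The cost is one or two extra items on the form with their dictionary entries, and one sentence on the denominator. Onset in hours will sometimes be missing, since follow-up and data capture rely on routine records.

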2. Intraoperative antibiotics*	
Yes (Prophylactic / Intraoperative spillage / Cholecystitis) / No *Defined as administration of antibiotics at least 30 minutes prior to skin incision to end of operation

3. Primary operator	
Consultant or attending Senior trainee (i.e., senior registrar or resident with >4 years surgical training/residency) Junior trainee (i.e., junior registrar or resident with ≤ 4 years surgical training/residency) Non-surgeon (e.g., medical practitioner or nurse)
 
If Consultant: What specialty? (General / Oesophago-gastric (OG) / HPB / Colorectal / Breast / Vascular / Other) If Trainee: Was this a training operation? (Yes / No). Was a consultant present? (Yes / No) If any: Number of cholecystectomies performed prior to this procedure: 0-50 / 51-100 / 101-200 / >200

4. Operative approach	
Open / Open conversion / Laparoscopic (Standard / Single Incision Laparoscopic Surgery (SILS)) / Robotic (Standard / SILS)
 
 If open, why: No laparoscopic equipment / Surgeon not trained in laparoscopy / Laparoscopy equipment broken / Multiple previous surgery / Disease severity. If open conversion, why: Suboptimal view / Adhesions / Not able to safely dissect CVS / Suspected bile duct injury / Patient unable to tolerate pneumoperitoneum / Bleeding / Bowel injury / Laparoscopic or robotic equipment failure / Suspected or actual cholecystoduodenal or cholecystocolonic fistula. If laparoscopic or robotic: was this gasless (Yes / No), were reusable equipment used? (Yes / No).
5. Intra-operative difficulty score – this is for minimally invasive surgery	
I / II / III / IV / V (Nassar Grade: Appendix D for definitions)

6. Was the Critical View of Safety (CVS) obtained (all three) – this is for minimally invasive surgery	
Yes / No If no, which criteria was met: 1) Clearing fat and fibrous tissue from the hepatocystic triangle.

	2) The lower third of the gallbladder being cleared from the cystic plate. 3) Only two structures are attached to the gallbladder.
7. Was there a time-out to verify CVS	Yes / No Defined as a momentary pause that what one is seeing is likely the correct anatomy

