8. Operation performed	Standard total cholecystectomy Total cholecystectomy by the fundus-first (top down) approach Subtotal cholecystectomy (reconstituting / fenestrated) Not performed (diagnostic laparoscopy / cholecystostomy) Definitions of subtotal cholecystectomy: 
 Fenestrated: does not occlude the gallbladder but may suture the cystic duct internally Reconstituting: closes off the lower end of the gallbladder, creating a remnant gallbladder
9. Abdominal drain insertion	Yes / No
10. Anatomical Biliary variant	Yes / No
11. Intraoperative CBD Assessment	Intraoperative cholangiogram (IOC) / Incisionless fluorescent cholangiography/ Laparoscopic ultrasound / Intraoperative ERCP If yes to any of the above: 
 Decision: Selective / Routine. If selective, state Indication: Raised liver function test / Concern of a bile duct injury / pre-operative imaging suggestive of CBD stone Findings: Stone / No stone. If stone, tick all that apply for management: Flushing with saline and smooth muscle relaxant / Fogarty catheter trawl / Basket retrieval / Choledochoscope / No intraoperative treatment attempted
12. Common Bile Duct exploration	Yes (Trancystic / Choledochotomy) / No If Choledochotomy then select closure: Primary closure / T-tube
13. Operative contamination	Clean (Gastrointestinal (GI) and genitourinary (GU) tract not entered) Clean-Contaminated (GI or GU tracts entered but no gross contamination) Contaminated (GI or GU tracts entered with gross spillage or major break in sterile technique) Dirty (There is already contamination prior to operation, e.g., faeces or bile).
14. Intraoperative complications - excluding bile duct injury (BDI) (Select all that apply)	Bile spilt / Stones Spilt / Bleeding / Major vascular injury / Bowel injury
15. Were reusable gowns used in this procedure?	Yes (All scrubbed staff/ some scrubbed staff) / No
16. Were reusable drapes used in this procedure?	Yes / No
30-day Outcomes	Required data (definition / comment)
1. Highest 30-day Clavien-Dindo (CD) Grade	0 / I / II / IIIa / IIIb / IVa / IVb / V (Appendix D for definitions) If CD IIIa: Radiological drainage (yes / No) If CD IIIb: Re-laparoscopy (yes / No) If CD V (death): please indicate time from index cholecystectomy to death: number of days (whole number, 0 = same day)

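### Bailout standard (Intra-operative 3): no field records whether the biliary anatomy was defined, so the patients the standard covers cannot be identified

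*Protocol*

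**What the plan says.** Under Statistical Considerations, Primary Outcome Measure, the protocol states: "The primary endpoint of this study is the compliance to pre-, intra-, and post-operative audit standards". One of these is Intra-operative standard 3, Bailout Procedures. Its trigger, for laparoscopic operations, reads "When CVS cannot be achieved and the biliary anatomy cannot be clearly defined by other methods (e.g. imaging", and the action that follows is "consider a bailout procedure (e.g. subtotal cholecystectomy or total cholecystectomy by the fundus-first (top down) approach". The trigger has two parts, and both must hold.

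The intra-operative fields of Appendix B (mirrored in the Appendix A form) that bear on this are:

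- Item 6, "Was the Critical View of Safety (CVS) obtained (all three", answered Yes or No, with the criteria met if No. This covers the first part of the trigger.
- Item 8, the operation performed (standard total, fundus-first total, subtotal, not performed). This covers the action.
- Item 10, "Anatomical Biliary variant", answered Yes or No.
- Item 11, the imaging modality used, whether selective or routine, and the indication if selective: "Raised liver function test / Concern of a bile duct injury / pre-operative imaging suggestive of CBD stone". The result is coded "Findings: Stone / No stone".

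Data Analysis & Sample Size plans a test of variation across HDI groups. It states no denominator for this standard.

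**The concern.** The second part of the trigger has no field. Item 11 gives the result of imaging in terms of stones, not anatomy, although Intra-operative standard 2 lists showing the anatomy among the purposes of imaging. The list of indications has no entry for unclear anatomy or failed CVS. Item 10 says whether a variant was present, not whether the anatomy was established.

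A patient with CVS = No who was imaged and had a standard total cholecystectomy may be exempt (imaging settled the anatomy) or covered without a bailout (imaging did not). The data look the same in both cases.

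The primary aim is to describe global variation in compliance. The site survey in Appendix C asks each hospital about access to and supply of intraoperative cholangiography, so imaging is expected to differ by setting. Wrong classification of imaged patients would differ with it. The adjustment variables named under Control of Bias and Confounding include neither imaging nor its result. The secondary endpoint on bailout procedures has the same gap.

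**Working it through.** **Tracing the standard to the form**

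| Element of the standard | Field | Recorded? |
|---|---|---|
| CVS not obtained | Item 6 | Yes |
| Anatomy not made clear by another method | none | No |
| Bailout performed | Item 8 | Yes |
| Bailout considered | none | No |

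**Effect of the choice of denominator**

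The protocol gives no CVS failure rate, imaging rate or bailout rate, so there is no figure to reproduce. All inputs below are assumptions, and imaging is taken as the only other method that defines the anatomy.

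- `i`: share of CVS = No patients imaged; 10% in one setting, 60% in the other
- `d`: share of imaged patients whose anatomy is defined; 50% to 80%
- `c`: bailout rate in covered patients, the same in both settings; 60% or 90%
- `b`: bailout rate in exempt patients; 0% to 30%

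The form allows at least three scorings:

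- A, all CVS = No: `(1 − i·d)·c + i·d·b`
- B, CVS = No and not imaged: `c`
- C, all CVS = No, every imaged patient counted as compliant: `(1 − i)·c + i`

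With c = 90%, d = 80%, b = 10%:

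- A, 10% imaged: 0.92 × 0.90 + 0.08 × 0.10 = 83.6%
- A, 60% imaged: 0.52 × 0.90 + 0.48 × 0.10 = 51.6%
- B: 90% in both
- C: 0.9 × 0.90 + 0.1 = 91%, against 0.4 × 0.90 + 0.6 = 96%

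With c = 60%, C gives 0.9 × 0.60 + 0.1 = 64% against 0.4 × 0.60 + 0.6 = 84%.

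Under A the gap between the settings is `(0.60 − 0.10)·d·(c − b)`:

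| c | Smallest gap (d = 50%, b = 30%) | Largest gap (d = 80%, b = 0%) |
|---|---|---|
| 60% | 0.5 × 0.5 × 0.3 = 7.5 points | 0.5 × 0.8 × 0.6 = 24 points |
| 90% | 0.5 × 0.5 × 0.6 = 15 points | 0.5 × 0.8 × 0.9 = 36 points |

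The gap is zero if b = c.

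**Why B is not a safe default**

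B discards patients whose imaging failed to settle the anatomy, and these are covered by the standard. Take i = 60%, d = 80%, bailout of 90% in non-imaged patients and 50% after failed imaging. Covered patients are 0.40 + 0.60 × 0.20 = 0.52 of the CVS = No group. True compliance is (0.40 × 0.90 + 0.12 × 0.50) / 0.52 = 80.8%, while B shows 90%.

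**The case against.** The protocol fixes no denominator and nowhere says that CVS = No followed by a standard total cholecystectomy counts as a failure. Scoring rules usually belong in the SAP, which was not available here. That stands: the protocol cannot be charged with a wrong denominator. It does not remove the gap, because an SAP can choose a rule but cannot supply the missing fact.

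A reader might infer that hospitals which image will look worse, or that CVS = No is the only denominator the data permit. The documents support neither. Scoring B uses the same form and gives no gap in the illustration, and scoring C reverses the direction. Scoring A produces the deficit only if exempt patients have bailout less often than covered ones.

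Nor are exempt patients confined to hospitals that image. The standard names imaging only as an example, so the anatomy may be settled another way.

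Some existing fields are informative. The Nassar grade (item 5, Appendix D) has a grade for a cystic pedicle that cannot be clarified, item 6 lists which CVS criteria were met, and item 11 separates concern about duct injury from suspected stones. These can support sensitivity analyses. None says whether the anatomy was eventually defined.

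The standard asks only that a bailout be considered, which is not recorded either. Exact compliance would therefore stay out of reach even with the missing field. The protocol also says that attainment of some standards will not be treated as a definitive measure of quality. Both points temper the consequence, but the covered population remains unidentified.

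**Conclusion.** The point holds in a limited form. The patients to whom Intra-operative standard 3 applies cannot be identified from the planned data, and this standard is one component of the primary endpoint. Its comparison across HDI groups will depend on an arbitrary treatment of imaged patients.

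The direction is conditional. If all CVS = No patients form the denominator, and exempt patients have bailout less often than covered ones, settings that image more will look less compliant. Other scorings give no gap or the opposite one. The spread of 7.5 to 36 points under scoring A shows only that the choice can matter; every rate behind it is assumed. This is a cheap improvement to one standard and does not put the whole endpoint in doubt.

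**What to change.** Add one item to Appendices A and B, asked only when CVS = No: *Biliary anatomy clearly defined by imaging or another method: Yes / No / Not attempted*. Define the denominator for Intra-operative standard 3 as CVS = No with the answer No or Not attempted. In the illustration, both settings then show their true value whatever their imaging rate.

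If the form can no longer be changed:

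- Report bailout among CVS = No patients separately for imaged and non-imaged cases.
- Give a range for compliance, treating all and then none of the imaged patients as exempt. In the worked example this is 83.6% to 90% in the setting that images 10%, and 51.6% to 90% in the one that images 60%.
- Say what the range assumes. It contains the true figure if non-imaged patients are all covered, covered imaged patients have bailout no more often than non-imaged ones, and exempt patients have it less often than covered ones.
- Do not use non-imaged cases alone as the main denominator.

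In either case, state that the data show the bailout performed, not whether one was considered.

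The cost is one tick-box for the patients without CVS or, on the fallback, a range in place of a single compliance figure.
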